strength and type of Internet connections they have available to them. Using their personal computer, participants receive a link via email to a videoconference. The success of signing on and completing a short call via videoconference will serve several purposes. First, it will allow for the research team to determine how comfortable the participant and communication partner are with using a computer and email to start a video-chat. Secondly, the audio/video guality of the video-chat will be a good indicator of the participant and communication partner's strength and quality of Internet connection. During the session, participants and communication partners will also be asked to complete an Internet speed test (www.speedtest.net) to ensure their Internet bandwidth can support uninterrupted video-chat. Participants are required to have at least 1 Mbps upload and 4 Mbps download of available Internet bandwidth as recommended by the HIPAA compliant video-chat software program used in this study. A strong Internet connection is important to ensure uninterrupted Treatment Sessions with consistent audio and video feed. Insufficient Internet connection will be remedied prior to enrollment. A Technology Proficiency screening was implemented during our preliminary study and has been successful at identifying appropriate candidates for treatment over videoconference.

Cognitive Screening. A brief cognitive screening (about 30 minutes) will be administered to participants over videoconference. This assessment will serve to confirm mild impairment of PPA.

Depression Screening. Individuals will be given the 15-item Geriatric Depression Scale to screen for depression. Indications of depression are categorized into mild, moderate and severe as follows: 5-8 mild depression, 9-11 moderate depression, and 12-15 severe depression; Sheikh & Yesavage, 1986). If an individual scores a 9 or above and their depression is untreated, they will be ineligible for the study.

SLP Screening. The screening with the speech-language therapist will be the last screening activity. SLP's will confirm PPA subtype at this screening.

At any point during screening, a participant may be determined to be ineligible. They will be informed of the reason they are ineligible for the study. If a participant is eligible, they will be consented into the study and randomized to study group (experimental vs. control).

Inclusion/Exclusion Criteria:

- Must be English speakers

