The individuals from OHSU are clinicians on the current study. However, all hard copies of data and coordination for the study will take place at NU. All recruitment will come from NU and then participants will be assigned to one of the clinicians. Enrollment decisions will be made by the team at NU. We are using these clinicians because they are experts in treating individuals with primary progressive aphasia, which is rare in the speech pathology field. If individuals are referred from OHSU, the NU team will complete all screening procedures to determine eligibility for the study.

The researchers joining us from OHSU ([name], M.S., CCC-SLP, speech-pathologist) who will be seeing patients is a Co-Investigator on the study. [name] (Co-Investigator) on the study will also be covered by this IAA. She will not see patients for the study, but is a part of the study team who will have access to participant data. [name]'s interactions with participants, and [name]'s data access for this study will be overseen by the Northwestern IRB. An IAA between Northwestern University and OHSU has been established between the two universities IRBs.

STUDY TIMELINES:

Participant participation in this study will last 1 year.

90 participants are intended to be enrolled over 5 years.

STUDY ENDPOINTS:

The primary endpoint of being able to discern differences between the treatment groups will occur when all 90 participants complete the research protocol. We intend to have the majority of patients (80/90) to have completed the interventions by the end of year 4.

PROCEDURES INVOLVED:

Study Design. Up to 100 participants will be randomized, 60% to the experimental group and 40% to the control group. The rationale for using an unequal enrollment design is to maximize the number of observations in the Experimental group for individuals with PPA, which may allow for further refinement and may mitigate study drop-out rates. Randomization will be blocked and stratified by subtype (PPA-L, PPA-G, PPA-S). Within each subtype, blocks will maintain the 60%:40% split of experimental:control, respectively.

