Post-Intervention Evaluation 2: This evaluation will be identical to the **Post-Intervention Evaluation 1** in Block 1. This evaluation will take place approximately one week following the 5 weekly therapy sessions of Intervention Block 2. Identical to other evaluations, this will occur over two sessions lasting no more than 2 hours per session (4 hours in total).

12- month Evaluation: Approximately one year after the Baseline Evaluation, the participant will take part in a final evaluation. Post-treatment outcomes will be measured through standardized evaluation measures, communication participation measures, and language performance measures that have been given throughout the course of the study. Identical to other evaluations, this will occur over two sessions lasting no more than 2 hours per session (4 hours in total).

Scheduling Compliance:

Sessions: To successfully complete the trial, participants must complete 10 visits within 12 weeks for the first treatment block and 5 visits within 7 weeks for the second treatment block. Circumstances may arise that require the re-scheduling of visits. When this occurs, the following rules apply:

- No more than 2 visits may be scheduled within a 5-day window
- Sessions on consecutive days should be avoided

Visits that cannot be scheduled within these rules will be considered 'missed' visits. In the case of a missed visit, the visit will not be re-scheduled. Dosing effects resulting from missed visits will be accounted for in the statistical analyses. Participants with more than 2 missed visits will be asked if they would like to continue to receive the intervention as part of routine clinical care; however, the participant will be withdrawn from the study analysis.

6-Month and 12-Month Evaluations: These evaluations should be scheduled within a time window that includes the 2-weeks prior to or following the actual 6 or 12 month follow-up date.

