Aim 1: Determine the within-group response of the Experimental and Control treatments for adults with PPA. Aim 1a will provide a descriptive and quantitative characterization of the response to treatment including within- group effect sizes.

Statistical analysis Aim 1a: The primary analysis goals for Aim 1a will be (i) the estimation of the within-person change and the variability in this change along with the statistical significance of the change within each treatment group and (ii) the estimation of the within-group effect size for each treatment group. These analyses will be done for all outcomes.

Power calculation for Aim 1: In preliminary data, the Pearson correlation between the initial and 6 month CCRSA was 0.70. Assuming a standard deviation of σ for an outcome at one time, and assuming a correlation of 0.50 between the initial and 12 month measure (since follow-up is longer), then the standard deviation of the change is also σ . Similar assumptions will be made for all outcomes. The Experimental group with a sample size of 51 would have 80% power to detect a mean change that is 0.4 σ while the Control group with a sample size of 34 would have 80% power to detect a mean change of 0.5 σ . For testing correlations between the change in an outcome and a continuous measure, the Experimental group (n=51) would have 80% power to detect a correlation of 0.38 while the Control group (n=34) would have 80% power to detect a correlation of 0.46. Two-tailed tests and a Type I error rate of 5% are assumed for all calculations for Aim 1.

Aim 2: Determine if a person-centered dynamic treatment approach (Experimental) for adults with PPA will show more favorable communication participation outcomes as compared to an impairment-only treatment approach (Control) over a 12-month course of disease.

Specific Aim 2 Analysis: The group statistical analysis will focus on two participation measures (CCRSA, Goal Attainment Scaling [GAS]) and two language performance measures (% target word accuracy and % script accuracy). All outcomes are continuous measures except for GAS which is ordinal. The primary analyses will focus on the initial and 12-month time points. Secondary analyses will be done using all time points, specifying certain post-hoc comparisons of interest (e.g. comparing the effect of the preand post-evaluations for the 6-month Treatment Sessions between groups).

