Power Calculation for Aim 2: Power will be based on a sample size of 51 in the Experimental arm and 34 in the Control arm. For all language and participation outcomes, preliminary data were used to estimate unadjusted standard deviations (SDs). It is expected that analysis of covariance would reduce the unadjusted SDs but since longitudinal data were not available on all measures, the conservative approach will be to use the unadjusted SDs in the power calculation. The Table below gives the between-group effect size (in units of the scale) detectable with 80% power for each outcome measure using a two-tailed test and a Type I error rate of 0.017. For example, for the CCRSA scale, there is 80% power to detect an Experimental minus Control difference of 12% in the 12-month mean adjusted by analysis of covariance for the initial evaluation CCRSA level.

Measure	Туре	SD	Between-group effect size with n=51 and 34 per arm ^A
Lexical Retrieval	Language	19 16	13
Script Performance	Language	14 25	10
Confidence Rating Scale for Aphasia (CCRSA)	Participation	16 16	12
Goal Attainment Scaling (T-Score)	Participation	10 26	7
^A 80% power, 2-tailed p<0.025 for language measures and $p<0.017$ for participation measures			

Table 1. Power Calculations

All members of the study team will be trained on the procedures of how data are stored and managed. Members of the study team that are approved by the Northwestern IRB will have access to the REDcap database and to the web-application database. All access to these applications will be provided over encrypted-TLS communication and all servers are locked and managed in a physically secure facility with Marlok identity management. All data will be de-identified and stored as much.

All data will be checked by a research assistant who is different from the individual who administered the tests. This checking will take place on hard copies of outcome measures and data stored in REDcap. Discrepancies between raters will be recorded by a crossing out of original score and initialing the new score with the checkers initials. REDcap includes a feature where data can be marked as "unchecked" or "checked". Once data are checked by a second scorer, they will be marked as "checked" in REDcap.

Participants will be asked if they are willing to share data from the study with other researchers within the CNADC. If so, researchers will not receive any identifiable information.

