Participants will be recruited through the following sources: Clinical Core participants at the Alzheimer's Disease Centers at Northwestern University (NU) and Oregon Health & Science University (OHSU), clinical referral (including NU and OHSU Clinics), Clinicaltrials.gov, NUCATS, the Alzheimer's Association TrialMatch website, as well as the Association for Frontotemporal Degeneration (AFTD).

All sessions for the intervention will take place remotely over a HIPAA compliant videoconferencing program. Therefore, participants will be located all over the United States. We will also enroll international participants.

RESOURCES AVAILABLE:

The Mesulam Center for Cognitive Neurology and Alzheimer's Disease, where this research will take place, is one of approximately 30 NIH-funded AD Centers and the investigators on this proposal are experts in neurodegenerative dementia syndromes including PPA, which was initially described in the modern literature by [name] (project Co-I and CNADC Director). The CNADC has one of the largest research programs for PPA. The current project will leverage the existing infrastructure of the CNADC and its affiliated grants. The CNADC PPA Research Program has enrolled and followed over 150 PPA participants and communication partners, who come from across the United States and Canada. Enrollment by PPA subtype has been relatively equal in our PPA research program. Retention has been excellent and the PPA Research Program has been highly successful yielding over 50 peer-reviewed publications that have made important contributions to the understanding of the disease, its diagnosis, and also in providing education and support to individuals with a dementia diagnosis, their families and professionals.

The investigators are well equipped to conduct this trial since they have expertise in developing web-based Behavioral Intervention Technologies (BITs) that help people make

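### Randomisation is stratified by PPA subtype, but no Aim 2 text puts subtype in the model; if subtype is prognostic, the 12-month test is slightly conservative

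*Combined protocol and SAP*

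**What the plan says.** Under Procedures Involved, the Study Design paragraph says "Randomization will be blocked and stratified by subtype (PPA-L, PPA-G, PPA-S"), and then: "Within each subtype, blocks will maintain the 60%:40% split of experimental:control, respectively". Subtype is known before allocation. Under SLP Screening, the last screening step, "SLP's will confirm PPA subtype at this screening", and randomisation follows for those found eligible.

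Specific Aim 2 Analysis lists four outcomes: CCRSA, Goal Attainment Scaling (GAS), target word accuracy and script accuracy. It describes all but GAS as continuous and GAS as ordinal. On timing it says "The primary analyses will focus on the initial and 12-month time points". It names no model and no covariates.

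A model appears only in Power Calculation for Aim 2, where the worked CCRSA example refers to a difference in the "12-month mean adjusted by analysis of covariance for the initial evaluation CCRSA level". Subtype is not mentioned there. Elsewhere it appears in Aim 1b, as one possible influence on the size of the treatment response within groups.

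**The concern.** Stratifying by subtype balances the arms within each subtype. Any effect of subtype on the 12-month score is therefore largely removed from the difference between arms. A model without subtype still counts that effect as residual noise, so it reports a standard error larger than the true sampling error of the estimate. The confidence interval is then wider than the design justifies, and the test rejects less often than its nominal level.

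What is at stake is precision. PPA is rare, the power calculation rests on 85 participants, and the CCRSA test is set at 0.017. The information that would recover the lost precision is already collected before randomisation.

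**Working it through.** **Inputs.** From Power Calculation for Aim 2 and Table 1: 51 and 34 participants, CCRSA SD 16 (the second 16 in that cell is read as a reference number), two-sided alpha 0.017, 80% power, detectable difference 12. From Power calculation for Aim 1: a correlation of 0.50 between the initial and 12-month values. That section adds "Similar assumptions will be made for all outcomes", but it was written for Aim 1 and is borrowed here. CCRSA is used because the text and the table footnote agree on 0.017 for it; for the language measures the text gives 0.017 and the footnote 0.025.

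**Assumption.** Let R² be the share of the residual variance, after adjustment for the initial value, that subtype explains. The documents give no figure, so 2%, 5% and 10% are shown.

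**Step 1: the plan's own figure.** k = √(1/51 + 1/34) = 0.2214. Detectable difference on the unadjusted SD = 16 × 0.2214 × (2.387 + 0.842) = 11.44 with normal quantiles, and 11.64 with the noncentral t. Either rounds up or off to the plan's 12 (11.64 directly). The figure is reproduced, and it takes no credit for covariate adjustment.

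**Step 2: baseline-only ANCOVA.** Reported SE = 16 × √(1 − 0.5²) × 0.2214 = 3.068. Residual degrees of freedom are 85 − 3 = 82.

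**Step 3: true SE under stratified allocation.** This is 3.068 × √(1 − R²) = 3.037, 2.990 and 2.910.

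**Step 4: actual Type I error without subtype.** This is 2 × P(Z > 2.387/√(1 − R²)) = 0.0159, 0.0143 and 0.0119. Simulation with t tests and exact 60:40 allocation in strata of 30, 30 and 25 (400,000 null runs) gave 0.0157, 0.0143 and 0.0118 without subtype, and 0.0167, 0.0168 and 0.0167 with it. The near-equal strata are an assumption, in line with the statement in Resources Available that "Enrollment by PPA subtype has been relatively equal in our PPA research program".

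**Step 5: where the conservatism comes from.** At R² = 0.20, simulated size of the baseline-only model was 0.009 with stratified allocation and 0.017 with unstratified allocation. The loss comes from stratifying and then leaving the factor out.

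**Step 6: difference detectable with 80% power, and power at 12.** Both use the noncentral t with noncentrality d / (3.068 × √(1 − R²)). Without subtype, the critical value is t(82 df)/√(1 − R²). With subtype, it is t on 85 − 5 = 80 df.

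| R² | Without subtype | With subtype | Gain (points) | Rise in power at 12 |
|---|---|---|---|---|
| 2% | 10.05 | 9.98 | 0.07 | about 0.3 |
| 5% | 10.02 | 9.83 | 0.19 | about 0.8 |
| 10% | 9.95 | 9.57 | 0.38 | about 1.5 |

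The last column is in percentage points. Power at 12 without subtype is about 93-94%.

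Hand check of the gain with normal quantiles: 2.387 × 3.068 × (1 − √(1 − R²)) = 7.323 × 0.01005, 0.02532 and 0.05132 = 0.07, 0.19 and 0.38.

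**Step 7: if subtype explains nothing.** Simulated power at a difference of 9.90 was 77.70% without subtype and 77.64% with it, a cost of under 0.1 percentage point.

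**The case against.** The strongest reply is that the ANCOVA is only an example in a power paragraph. The analysis section names no model, and nothing says that the initial value is the only covariate. This stands. A reader might infer that the sponsor has settled on a baseline-only primary model, but the documents do not go that far, so the finding is conditional on that model being used. The reply does not remove the gap: if the example is not the plan, the documents state no Aim 2 model at all.

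Second, nothing shows that subtype is prognostic. Aim 1b concerns treatment response within groups, which is not the same as predicting the 12-month score. This also stands. R² near zero is compatible with the documents, and then nothing is gained.

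Third, the benefit is small where the plan is powered. At a difference of 12 it is 1.5 percentage points or less over the assumed range. This is correct and sets the severity.

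Fourth, for GAS the remedy is not neutral. In an ordinal logistic model, adding subtype changes the odds ratio to one conditional on subtype. This stands and is carried into the fix.

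**Conclusion.** The concern holds in a limited form. If the named ANCOVA is used without subtype, and subtype predicts the 12-month CCRSA beyond the initial value, the test is conservative: actual Type I error is about 0.016 to 0.012 against a nominal 0.017. The precision forgone is worth 0.07 to 0.38 CCRSA points. These sizes rest on the assumed R² of 2% to 10%, the borrowed correlation of 0.50, and 85 analysed participants. That number is the basis of the power calculation and not a fixed sample size; the plan also gives 90 intended and up to 100 randomised. The direction is firm; the size is not known.

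A reader might infer that the primary test is invalid or that the power is overstated. Neither follows. Omitting the stratifier lowers the Type I error, and the stated power uses unadjusted SDs. A reader might also extend the point to missing 12-month scores or to the rules on withdrawal from analysis; those are separate questions that this calculation does not address. Severity is minor.

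**What to change.** In Specific Aim 2 Analysis, state the primary model for each continuous outcome: an ANCOVA of the 12-month score with treatment, the initial value and PPA subtype as terms, using the subtype recorded for stratification. For GAS, name the model and account for subtype in it as well. If that model is ordinal logistic, say that the treatment odds ratio is conditional on subtype.

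The cost is a sentence or two of analysis text and two degrees of freedom. It needs no new data and no change to the sample size, and for the continuous outcomes the 12-month comparison between arms stays the same.

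### If Aim 2 is tested at the fixed levels in the Table 1 footnote, Holm's step-down within each family would recover some power at the same within-family error rate

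*Combined protocol and SAP*

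**What the plan says.** Under Specific Aim 2 Analysis, the protocol names two participation measures (CCRSA and Goal Attainment Scaling) and two language measures (target-word accuracy and script accuracy). It gives no rule for handling the several tests.

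Significance levels appear only under Power Calculation for Aim 2. The Table 1 footnote reads "80% power, 2-tailed p<0.025 for language measures" and goes on to set 0.017 for participation measures. The sentence above the table gives one level for every outcome: "using a two-tailed test and a Type I error rate of 0.017". The basis is "Power will be based on a sample size of 51 in the Experimental arm and 34 in the Control arm".

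Neither Bonferroni nor any step-down method is named anywhere. In the Objectives, Hypothesis 3 predicts a between-group benefit on communication participation only.

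**The concern.** The footnote levels are 5% divided by two and, after rounding, by three. Read as decision rules, they hold each measure to its own share whatever the other measure in the family shows. Holm's step-down tests the smallest p-value at that same share. If it is rejected, the next is tested at a larger share. Holm controls the family-wise error under any correlation and never rejects less than the fixed split.

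Under the fixed rule, a second language measure with p between 0.025 and 0.05 would be declared negative even when the first had passed, with no added protection within the family. With 51 + 34 = 85 participants and a design set at 80% power per measure, that is power given up for little return.

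**Working it through.** **Inputs.** From Table 1 and its footnote: n = 51 and 34; 80% power; two-sided levels 0.025 (language) and 0.017 (participation); SDs 19, 14, 16 and 10, reading the second number in each SD cell as a citation. The correlation between measures is not in the documents. It is assumed, over 0 to 0.8.

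**Step 1: reproduce Table 1.** Detectable difference = (z for the level + 0.842) × SD × √(1/51 + 1/34), where the root is 0.2214, z(0.025) = 2.241 and z(0.017) = 2.387. The t version uses 83 df.

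| Measure | Level | Normal | t | Stated |
|---|---|---|---|---|
| Lexical retrieval | 0.025 | 12.97 | 13.17 | 13 |
| Script | 0.025 | 9.56 | 9.70 | 10 |
| CCRSA | 0.017 | 11.44 | 11.64 | 12 |
| GAS | 0.017 | 7.15 | 7.27 | 7 |

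The t values all round to the stated figures. At 0.017, lexical retrieval would need 13.6 to 13.8, which rounds to 14. So the table was built on the footnote's levels and not on the single 0.017 in the text.

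**Step 2: Holm by hand, independent measures, both effects at the 80% point.**

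Language: the standardised effect is 2.241 + 0.842 = 3.083. Power at 0.05 is Φ(3.083 − 1.960) = 0.869.
- Per measure: 0.80 + (0.869 − 0.80) × 0.80 = 0.855.
- Both, fixed: 0.80² = 0.64. Both, Holm: 0.869² − 0.069² = 0.75.

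Participation, with 0.017 then 0.025 (the first two steps of a three-test Holm): the effect is 2.387 + 0.842 = 3.229 (3.228 unrounded). Power at 0.025 is Φ(3.228 − 2.241) = 0.838.
- Per measure: 0.80 + 0.038 × 0.80 = 0.830.
- Both, fixed: 0.64. Both, Holm: 0.838² − 0.038² = 0.70.

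**Step 3: correlated measures, by simulation** (500,000 or more pairs of normal test statistics per setting).

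| Family | Correlation | Per measure, fixed → Holm | Both, fixed → Holm | At least one (same for both rules) |
|---|---|---|---|---|
| Language | 0 | 80% → 86% | 64% → 75% | 96% |
| Language | 0.5 | 80% → 85% | 69% → 78% | 91% |
| Language | 0.8 | 80% → 84% | 73% → 80% | 87% |
| Participation | 0 | 80% → 83% | 64% → 70% | 96% |
| Participation | 0.5 | 80% → 83% | 69% → 74% | 91% |
| Participation | 0.8 | 80% → 82% | 73% → 77% | 87% |

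With no true effect on either language measure, family-wise error is the same under both rules and at most 5%: 1 − 0.975² = 4.9% if independent, and about 4% at correlation 0.8.

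**Step 4: one measure with no effect.** Holm then helps the other only when the null measure is rejected. For language at correlation 0, power is 0.80 + 0.069 × 0.025 = 0.802. The gain is at most 0.3 points in every setting run.

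**Step 5: size of the participation family.** If it has only the two named measures, a two-test Holm (0.025, 0.05) gives 87-89% per measure. Part of that comes from spending the unused third share: a fixed 0.025 alone gives 84%.

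**Step 6: across families.** The fixed levels of the four named measures sum to 2 × 0.025 + 2 × 0.017 = 0.084. Holm within families does not change the lack of control across the two.

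**The case against.** *The procedure is inferred.* A level used in a power calculation does not commit the analysis to that fixed level, and 0.05/2 and 0.05/3 are also Holm's first-step levels. This stands: a reader might infer that the plan prescribes fixed Bonferroni tests, but the documents do not say so. The point is therefore conditional. It still has substance, because these are the only levels given for Aim 2.

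*The larger gain is in the wrong family.* Hypothesis 3 concerns participation. Hypothesis 1 expects controls to gain on language, and controls are trained on scripts and target words. Full between-group effects on both language measures are thus not the predicted scenario. This also stands. The gain for participation is smaller, 2 to 3 points per measure on the three-test reading.

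*The power basis is deliberately conservative.* The plan says "the conservative approach will be to use the unadjusted SDs in the power calculation". If the 0.50 correlation assumed for Aim 1 is applied, the SD shrinks by √(1 − 0.50²) = 0.866. At the 80% point, fixed-level language power becomes Φ(3.083/0.866 − 2.241) = 0.91. Holm then adds about 3 to 3.5 points per measure at correlations up to 0.5, and both declared rises from 82% to 89% (independent) or from 84% to 90% (correlation 0.5). The gain shrinks but does not vanish.

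*Fixed levels are valid and give simpler simultaneous intervals.* True. That is why this is an improvement and not a correction.

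**Conclusion.** The point holds conditionally and is minor. If Aim 2 is tested at the footnote's fixed levels, Holm within each family is at least as powerful at the same within-family error rate. With both effects real and at the 80% point, the gain per measure is about 4 to 6 points for language and 2 to 3 points for the two named participation measures under a three-test Holm. The chance of declaring both rises by about 7 to 11 and 4 to 6 points respectively.

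These sizes rest on an assumed correlation of 0 to 0.8 and on the Bonferroni reading of the levels. They fall to almost nothing if the other measure has no effect, and the chance of at least one success does not move.

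Two stronger inferences should be resisted. The language figures do not show what the trial loses on its main hypothesis, which concerns participation. Nor is Table 1 wrong: its figures reproduce at the footnote's levels.

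**What to change.** First, list the measures in each family. The 0.017 level implies three participation tests where two are named, and the text's 0.017 for all outcomes conflicts with the footnote's 0.025 for language. Reconcile both before Holm is defined.

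Then add to Specific Aim 2 Analysis, before outcome data are examined: *Within each family (participation, language), p-values are tested by Holm's step-down at two-sided 5%, and Holm-adjusted p-values are reported.* Keep Table 1, labelled as first-step power, provided the reconciled family sizes match its levels. State that error is controlled within families and not across them.

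The cost is a few sentences, with no change to sample size or data collection. The one drawback is that simultaneous confidence intervals become slightly less simple than under a fixed split.
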